## **Outcomes and Statistical Plan**

Data will be gathered based on the attached Data Collection Form (Appendix 2). Answers to the questionnaire will be deidentified.

Power calculations will be performed considering the primary endpoint of a dichotomous response to question #1 of the CG-CAHPS. Thirty subjects per group will be needed to achieve 80% power to detect a difference of 26% or more between proportions (hypothesized standard of care mask positive response rate of 73% versus clear mask positive response rate of 99%) with alpha of 5% using conservative two-sided Fisher's Exact Test. Therefore the enrollment goal will be 60 subjects total.

Secondary outcomes will include differences in response to the remaining quantitative questions of the CG-CAHPS and free text responses to the final question. As the quantitative question responses are on a Likert scale, responses 1-3 will be considered negative and 4 will be considered positive thereby converting the outcome to binary according to the top box method. Fisher's Exact Test will be used to investigate a difference between the standard of care mask and the clear mask for all dichotomous outcomes. P-values < 0.05 will be considered statistically significant. A content analysis will be performed on the free responses to investigate distinct themes.

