## **Interventions and Interactions**

Patients who both elect to undergo DBS surgery and agree to participate in this study will have a record created in the study database. All patients scheduled for a DBS phase I surgery will be contacted via telephone in the days prior to their scheduled surgery to discuss the possibility of study participation. This will be done to give the patient time to consider study participation in order to avoid delays the morning of surgery. The morning of surgery the patient will be approached in pre-operative holding room to discuss participation in the study and if amenable sign consent for participation. This discussion will inform the patient that minor changes are being made in an attempt to improve the patient experience, but limited information regarding what steps exactly will be provided so as to reduce potential bias that might result from the patient knowing we are studying a new mask type. If the patient agrees to participation, a consent form will be signed and as a baseline will undergo the Hearing Handicap Inventory for the Elderly (HHIE-S) questionnaire before the operation (Appendix 1). The patient's record in the electronic study database will then be created and randomized to one of two groups. Group A will experience the neurologist wearing a clear mask, and group B will experience the neurologist wearing a standard covered mask. The patient and all other intra-operative personnel will wear a covered surgical mask.

Following standard surgical protocol, the DBS surgery will proceed with the patient awake. First, a stereotactic frame is securely attached to the patient's head and the patient is positioned appropriately. Local anesthetic is used for the neurosurgeon to obtain access through the scalp and skull. A microelectrode is then stereotactically placed using headframe coordinates. The neurosurgeon sets up the motor apparatus to allow the neurologist to advance the microelectrode to the appropriate deep brain target, operating the motor from a non-sterile station arranged next to the patient. The microelectrode will stimulate and record neuronal activity, during which time the neurologist will ask the patient questions to assess for changes in symptoms. These questions typically are of the following nature:

- Do you notice any tingling or pulling of the mouth or face?
- Do you see any flashes of light in your vision?
- Do you feel any tingling or heaviness of an arm or leg?

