At the conclusion of the neurologist's assessment, as is typical, the patient will be placed under sedation for the completion of the DBS implantation. In the event a patient is having bilateral DBS implantation in one operation, only the first DBS implantation will be included in the study. For these patients, the procedure will be carried out as stated above, but following the first DBS implantation the neurologist will continue to interact with the patient for the second DBS implantation. The second implantation will not be included in the study data collection.

A retrospective chart review will be conducted for the 30 day post-operative period to evaluate for surgery-related infection. Evaluating for rates of infection between mask groups will help to ensure there is no harm associated with use of a non-covered mask during the operation. The patients will not need to be contacted or otherwise actively participate in the study during this period; information will be obtained via medical record review only. For such a chart review, a waiver of consent will be completed in the IRB application. Such a waiver is necessary in order to answer the study question regarding mask safety and surgery-related infection, as it would be difficult to retrospectively re-consent every patient already enrolled in this nearly-complete study.

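### The stated 80% power for a 26-point difference or more holds only near the planned 73% versus 99%, and the primary analysis has no effect estimate or confidence interval

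*Combined protocol and SAP*

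**What the plan says.** All the statistical content is in the Outcomes and Statistical Plan section.

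- **Endpoint:** the "primary endpoint of a dichotomous response to question #1 of the CG-CAHPS". Only the top score of 4 counts as positive.
- **Power:** "Thirty subjects per group will be needed to achieve 80% power to detect a difference of 26% or more between proportions". A parenthesis in the same sentence gives the "hypothesized standard of care mask positive response rate of 73% versus clear mask positive response rate of 99" (per cent). The test is two-sided Fisher's exact at 5%, and the total is 60. No other pair of rates is given.
- **Analysis:** "Fisher's Exact Test will be used to investigate a difference between the standard of care mask and the clear mask for all dichotomous outcomes", with the rule "P-values < 0.05 will be considered statistically significant". No risk difference, ratio or confidence interval is named for the primary endpoint, here or elsewhere.

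The Interventions and Interactions section describes allocation as "The patient's record in the electronic study database will then be created and randomized to one of two groups" and mentions no blocking, so the realised split need not be 30/30. The same section calls the study nearly complete: "it would be difficult to retrospectively re-consent every patient already enrolled in this nearly-complete study".

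**The concern.** The power sentence is worded as a property of the difference alone. The variance of a proportion shrinks towards zero as the rate nears 100%, so a 26-point gap ending at 99% is much easier to detect than the same gap lower down. A reader who takes the sentence at face value would credit the trial with 80% power for any gap of that size.

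The second part is how a non-significant result would be read. With only a p-value beside a claim of 80% power for 26 points or more, such a result could be taken to exclude the benefit the trial was sized for. An effect estimate with an interval would show whether it does.

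**Working it through.** **Inputs from the Outcomes and Statistical Plan section.** 30 per group; standard rate p1 = 0.73; clear rate p2 = 0.99; two-sided Fisher's exact test; reject when p < 0.05. All other rates below are illustrative assumptions, because the documents give none.

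**Formula.** Power = Σ over all (x1, x2) of Bin(x1; n1, p1) × Bin(x2; n2, p2) × 1[Fisher p < 0.05].

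**Step 1: reproduce the plan's figure.** At 30/30, with x2 positives on the clear mask, Fisher's test rejects in favour of the clear mask when the standard-mask count x1 is at or below a cut-off:

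| x2 | P(x2) at 0.99 | cut-off for x1 | P(x1 ≤ cut-off) at 0.73 | product |
|---|---|---|---|---|
| 30 | 0.7397 | 24 | 0.8590 | 0.6354 |
| 29 | 0.2242 | 22 | 0.5853 | 0.1312 |
| 28 | 0.0328 | 21 | 0.4226 | 0.0139 |
| 27 | 0.0031 | 19 | 0.1613 | 0.0005 |

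The sum is 0.781; the remaining tables add nothing at this precision. At 31 per group the power is 80.5%. So the stated 80% with 30 per group is reproduced to within two points of power, or one patient per group.

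**Step 2: where the words 'or more' hold.** At 30/30 with one planned rate kept: 73 vs 100 gives 85.9%, 72 vs 99 gives 81.2% and 70 vs 99 gives 86.4%.

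**Step 3: the same 26 points at other rates.** Splits run from 25/35 to 35/25. The average is over simple randomisation of 60, n1 ~ Binomial(60, 0.5).

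| Standard vs clear | Gap | Power at 30/30 | Range over splits | Average |
|---|---|---|---|---|
| 73 vs 99 | 26 | 78.1% | 78.1–92.3% | 85.6% |
| 72 vs 98 | 26 | 74.4% | 74.4–88.2% | 81.5% |
| 70 vs 96 | 26 | 68.9% | 68.9–80.4% | 74.9% |
| 65 vs 91 | 26 | 59.4% | 59.4–66.1% | 63.7% |

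At 30/30 the gap needed for 80% power is 26.6 points when the clear rate is 99%, 27.8 at 98%, 28.8 at 97%, 30.5 at 95% and 33.6 at 90%.

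**Step 4: sensitivity to the 99% (a separate question).** Keep the standard rate at 73% and lower only the clear rate. Power at 30/30 is then 70.9% at 98%, 64.1% at 97% and 51.7% at 95%. These gaps are below 26 points.

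**Step 5: what a non-significant result leaves open.** With Wilson limits (l, u) for each arm and d = p̂2 − p̂1, the Newcombe interval is

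lower = d − √[(p̂2 − l2)² + (u1 − p̂1)²]; upper = d + √[(u2 − p̂2)² + (p̂1 − l1)²].

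Example: 22/30 standard against 27/30 clear. The Wilson limits are 0.556 to 0.858 and 0.744 to 0.965, and d = 0.167.

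- lower = 0.167 − √(0.156² + 0.125²) = −0.033
- upper = 0.167 + √(0.065² + 0.178²) = 0.356

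Fisher p is 0.18, and the interval, −3.3 to 35.6 points, includes 26.

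Over all 30/30 outcomes at 73 vs 99, 21.9% of trials are non-significant (1 − 0.781), and the interval includes 26 points in 89% of those.

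**The case against.** The strongest reply is that the power sentence contains its own qualification. The parenthesis names 73% and 99%, and with either rate kept, the words 'or more' are right (step 2). They fail only when both rates move down together, which the section does not expressly claim to cover. This largely stands. It makes the fault one of loose wording, but the main clause still speaks of a difference in general.

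Exactly 30/30 is also the least favourable split in the range examined, for every pair in the table. On average over simple randomisation, both 73 vs 99 and 72 vs 98 exceed 80%. That stands too. The plan itself names 30 per group, so 30/30 is a fair reference, and 65 vs 91 stays below 67% at every split examined.

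Three stronger readings are tempting, and the documents support none of them:

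- **That 60 patients is a wrong sample size.** The plan's figure is reproduced within tolerance.
- **That 52% power at 73 vs 95 contradicts the power sentence.** That gap is 22 points, outside what the sentence claims. It shows only how much rests on 99%, and nothing in the documents makes 95% more plausible than 99%.
- **That the investigators will read non-significance as no difference.** The plan does not say so. It only leaves out the quantity that would guard against it.

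Finally, an interval could simply be added at write-up. That is true, but naming the measure and method beforehand avoids a choice made after seeing the data.

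**Conclusion.** The concern holds as a minor one with two parts.

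1. The power claim is general in wording but holds only near 73% versus 99%. At 30 per group, a 26-point gap has 78% power at the planned rates, 69% at 70 vs 96 and 59% at 65 vs 91.
2. The primary analysis has no effect estimate or interval. About 22% of trials at the planned rates would be non-significant at 30/30, and about 89% of those would still be compatible with a 26-point benefit.

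These figures assume complete data, independent patients, two-sided Fisher's exact test with p < 0.05 and, unless stated otherwise, an exact 30/30 split. Rates other than 73% and 99% are illustrative.

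**What to change.** **Power sentence.** Drop the general claim about a 26-point difference or more, and state instead:

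> *Thirty per group gives about 78% power at exactly 30 per group for 73% versus 99% (two-sided Fisher's exact test, alpha 5%); power is lower for the same difference if the clear-mask rate is below 99% (for example 69% for 70% versus 96%).*

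**Primary analysis.** Add:

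> *The risk difference (clear minus standard) for the primary endpoint will be reported with a Newcombe 95% CI; Fisher's exact test decides significance, and a non-significant result will be interpreted from the interval.*

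**Cost.** One sentence is reworded and one added. The sample size, test and decision rule stay as they are, which suits a study near completion. There are two downsides. The stated power looks slightly less favourable. The interval can also exclude zero when Fisher p is 0.05 or more: this happens in 9.8% of trials at the planned rates with 30/30, for example 22/30 vs 28/30, with p = 0.080 and an interval of 0.7 to 38.4 points. That is why the added text names Fisher's test as decisive.

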- Do you notice any metallic or strange taste?
- Can you draw a spiral on this piece of paper?
- Can you hold your arm out in front of you and keep it still?

During a routine DBS surgery, the neurologist is positioned in view of the patient while operating the electrode motor and asking the above questions. Microelectrode stimulation and recording will conclude

when the appropriate target has been reached; that is, when simulation achieves both symptom improvement without new neurologic symptoms. At that point, the microelectrode is withdrawn and the macroelectrode is placed. The macroelectrode is stimulated in the determined position to again confirm symptom improvement without new neurologic symptom or deficit, and when confirmed the neurosurgeon will secure the macroelectrode in place. At this point, the neurologist's testing portion is complete, and the neurologist exits the operating room while the neurosurgeon completes the implantation.

For patients who agree to study participation, the neurologist will wear the mask type assigned by the randomization group for the duration of involvement in the surgery. At the conclusion of the neurologist's interaction with the patient, the patient will be asked a series of questions (presented in Appendix 2, Data collection form) to evaluate the communication experience. This step will be performed by another member of the study team (not the participating neurologist) who will read from the questionnaire and record the patient's responses using the Likert scale (defined in Appendix 2). During questioning, the neurologist will step out of the operating room to reduce potential bias from the patients answering subjective questions in front of the neurologist.

At the conclusion of the questionnaire, the patient will undergo a short debriefing regarding the aims of the study, specifically the revelation that the purpose of the study is to evaluate the use of a clear surgical mask on the patient's experience, as assessed by the questionnaire.

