## Appendix 2. Data collection form

Patient ID: \_\_\_\_\_

Neurologist: \_\_\_\_\_

Group Assignment:  A – Clear

B – Covered

**Mask type used:** Clear / Covered

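### Does the two-sided Fisher's exact test waste alpha that the trial should recover by switching to Boschloo's exact test?

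*Combined protocol and SAP*

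**What the plan says.** The Outcomes and Statistical Plan section makes the dichotomised answer to the first CG-CAHPS question the primary endpoint. It states: "Thirty subjects per group will be needed to achieve 80% power to detect a difference of 26% or more between proportions", with assumed positive response rates of 73% for the standard mask and 99% for the clear mask, "with alpha of 5% using conservative two-sided Fisher's Exact Test". The total is 60.

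The same section names the analysis test. Fisher's test "will be used to investigate a difference between the standard of care mask and the clear mask for all dichotomous outcomes", and "P-values < 0.05 will be considered statistically significant". Sizing and analysis therefore use one test at one level.

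Three other places bear on a change of test:

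- **Allocation.** In Interventions and Interactions, each patient's record "will then be created and randomized to one of two groups". No blocking or other method is given, so an exact 30/30 split is planned but not guaranteed.
- **Timing.** The paragraph there on the 30-day chart review refers to "every patient already enrolled in this nearly-complete study".
- **Who sees what.** On the questionnaire, the same section says "This step will be performed by another member of the study team", meaning someone other than the neurologist. The form in Appendix 2 holds the group assignment, a field headed "Mask type used" and all the answers.

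**The concern.** Fisher's test conditions on the total number of positive answers. With small arms few tables are possible, so its p-values move in large steps and its true type I error sits below the nominal level. At 30/30 the step is wide. Five negative answers on the standard mask against none on the clear mask gives p = 0.052, which misses significance. Six against none gives p = 0.024.

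Boschloo's test takes the Fisher p-value as its statistic and computes its exact distribution without conditioning, maximised over the unknown common rate. It also holds 5%, and it would declare the five-against-none table significant (p = 0.027). In a trial fixed at 60 patients with a single binary primary question, 9 points of power at no cost in patients looks like an omission. The stated 80% also appears slightly optimistic for the named test. If both points held as faults, the trial would run a needless risk of missing a real effect.

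**Working it through.** **Inputs.** n = 30 per arm, rates 0.73 (standard) and 0.99 (clear), two-sided test, reject if p < 0.05. All come from the Outcomes and Statistical Plan section.

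**Step 1: the plan's own figure.** Power is the sum, over k negative answers on the clear mask, of P(K = k) × P(M ≥ m_k). Here K is binomial(30, 0.01), M is binomial(30, 0.27), and m_k is the smallest number of negatives on the standard mask that gives Fisher p < 0.05.

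| k | m_k | Fisher p at m_k | P(K = k) | P(M ≥ m_k) | product |
|---|---|---|---|---|---|
| 0 | 6 | 0.024 | 0.7397 | 0.8590 | 0.6354 |
| 1 | 8 | 0.026 | 0.2242 | 0.5853 | 0.1312 |
| 2 | 9 | 0.042 | 0.0328 | 0.4226 | 0.0139 |
| 3 | 11 | 0.030 | 0.0031 | 0.1613 | 0.0005 |

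The sum is 0.781. At 31 per arm the same calculation gives 0.805. The stated 80% is met within 2 points and one patient per arm. Rounding of the assumed rates could account for the gap: 72.5% versus 99% gives 79.7%, and 73% versus 99.5% gives 81.9%. It can also go the other way, since 73.33% versus 99% gives 77.0%.

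**Step 2: is the test valid?** The largest rejection probability over a common rate at 30/30 is 2.74%, reached at a rate of 0.5. At unequal splits of 60 from 24/36 to 36/24 it is 3.5% to 3.9%. All are below 5%. The test errs only on the cautious side, and the plan says so.

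**Step 3: what would Boschloo's test gain?** Version A orders tables by the two-sided Fisher p-value. Version B doubles the smaller one-sided Boschloo p-value, as some software does. Power in percent at 73% versus 99%:

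| Standard/clear | Fisher | A | B | A − Fisher | B − Fisher |
|---|---|---|---|---|---|
| 28/32 | 90.9 | 90.9 | 86.8 | 0.0 | −4.1 |
| 29/31 | 92.3 | 92.4 | 85.8 | 0.0 | −6.6 |
| 30/30 | 78.1 | 87.4 | 87.4 | 9.3 | 9.3 |
| 31/29 | 81.0 | 89.3 | 89.2 | 8.3 | 8.2 |
| 32/28 | 83.6 | 90.9 | 88.0 | 7.3 | 4.5 |

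Differences are taken before rounding. Moving one patient from 30/30 to 29/31 removes the gain because Fisher itself then rejects four negatives against none. That table has probability C(29,4)/C(60,4) = 23,751/487,635 = 0.0487. The mirror table has C(31,4)/C(60,4) = 31,465/487,635 = 0.0645, which is larger and so is not added to the p-value. At 30/30 the two tails are equal and always add: 2 × C(30,5)/C(60,5) = 2 × 142,506/5,461,512 = 0.0522.

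If simple 1:1 randomisation is assumed, average power is 85.6% for Fisher and 89.4% for version A, a gain of 3.8 points. About half of the probability falls on splits where A gains less than 1 point.

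**Step 4: does the version matter?** At 29/31, 25 of 29 versus 31 of 31 positive gives p = 0.049 with Fisher, 0.039 with A and 0.055 with B. An unspecified Boschloo test could lose a result that Fisher finds.

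**Step 5: can the test still be changed?** The documents call the study nearly complete. Appendix 2 puts mask type beside the answers, and a study team member fills it in. No masking of staff to outcomes by arm is described. A switch at this point would move 25/30 versus 30/30 from p = 0.052 to 0.027, which is the kind of change that readers distrust when it comes late.

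**The case for a change.** The best case for switching is strong on arithmetic. Version A rejects every table that Fisher rejects at all 25 splits checked (18/42 to 42/18), keeps its size at or below 5%, and needs no extra patients. The planned 99% leaves little room. If the clear-mask rate were 95%, power at 30/30 would be about 52% with Fisher and 60% with version A. The gain can also exceed 9 points at other rates: 16.2 points at 30/30 for 80% versus 99%. The switch could be limited to the case where nobody has seen outcomes by arm, with the version named to avoid the loss in Step 4. Failing that, the power sentence could be restated as 78%.

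The figures stand, and at the design stage version A would have been a reasonable choice. They do not show a fault. The condition is hard to satisfy, because whoever completes the form sees arm and answer together for that patient. The documents neither confirm nor exclude that results by arm have been tabulated. A switch for question 1 alone would also give two items with identical counts different verdicts, because the other items would stay with Fisher. Restating 80% as 78% would alter no analysis and no conclusion.

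**Conclusion.** The concern does not hold. The plan names a valid exact test in advance, acknowledges its caution, and uses it for both sizing and analysis. Its stated power is right to within 2 points (78.1% against 80%) and one patient per arm. Preferring Boschloo's test is a choice between two valid methods. At 73% versus 99% and the splits of 60 examined, version A gains between nil and 9.3 points, and the alternative version can lose up to 6.6. With the trial nearly complete and no staff masking described, keeping the prespecified Fisher test is the sounder course.

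This rests on the planned rates, on all 60 patients being evaluable and, for the 3.8-point average, on simple randomisation, which the documents do not state.

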## **Human Subjects Protection**

### **Subject Recruitment Methods**

Selection of potential study participants will be based upon screening all patients who elect to undergo DBS placement during the enrollment period. The decision to undergo DBS placement will be made on an individual patient basis between patient/family and treating neurologist and neurosurgeon, without regard to consideration or participation in this study. These potential study participants will then be screened using inclusion and exclusion criteria above and approached for interest. If amenable, the purpose and steps of the study will be further explained, but without divulging the clear mask as the topic of study to avoid introducing bias with regard to mask type. If the participant gives consent, the consent form will be signed prior to any data collection or randomization. At the conclusion of the patient's study participation (i.e., the completion of the questionnaires intra-operatively) the purpose of the study will be fully explained to the patient.

